5.9.6. REDUCTION IN CYLINDER POWER

Reduction in cylinder power will be calculated for each eye implanted with the HMTIOL as follows:

Cylinder Power Reduction = absolute value of preoperative magnitude of corneal cylinder (K) – absolute postoperative magnitude of MRCYL at the corneal plane.

The percent reduction in cylindrical power will be calculated for eyes with non-zero preoperative corneal cylinder as follows:

Cylinder Power % Reduction = Cylinder Power Reduction/ absolute value of preoperative magnitude of corneal cylinder (K) $\times 100$.

Descriptive statistics for continuous variables will be used to summarize these outcomes at each visit.

6. Sample Size

Based on a one-sided two-sample non-inferiority t-test with a significance level of 0.05, a sample size of 25 bilateral subjects (50 total eyes, 25 in each cohort) with successful implants and 3-month follow-up ECC data for each eye provides a power of 80% to reject the null hypothesis if the true difference in mean ECC percent change is 5%, the standard deviation of the ECC percent change is 12.6%.

It should be noted that some study subjects may not have successful implants in both eyes due to intraoperative eligibility, or do not have the 3-month ECC data for both eyes. These subjects will be excluded from the ECC comparisons. With an assumption of a dropout rate of approximately 20%, a sample size of 32 bilateral subjects should be enrolled.

7. Analysis Populations

Subjects that are screened but disqualified based on the preoperative and intra-operative eligibility criteria will be excluded from the safety and performance data analyses. However, their reasons for the screen failure will be summarized. The analyses populations are defined below.

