	
15. Taking systemic medications that, in the opinion of the investigator, may confound the outcome or increase the intraoperative and post-operative risk to the subject (e.g. Tamsulosin Hydrochloride – Flomax) or other medications including anticholinergics, alpha adrenergic blocking agents with similar side effects (e.g. small pupil/floppy iris syndrome)
 
Exclusion Criteria During Surgery
 
 
1. Vitreous loss prior to use of the investigational device
 
2. Positive posterior pressure preventing safe implantation of the lens system
 
3. Anterior chamber hyphema preventing visualization of implantation
 
4. Any zonular or capsular rupture or capsular bag instability
 
5. Intraoperative miosis preventing visualization of fixation features
 
6. Need for concomitant procedures (e.g. glaucoma surgery, LRI, RK, LASIK, etc.)
 
 
Subject who, in the clinical judgment of the investigator, is not suitable for participation in the study for another clinical reason, as documented by the investigator

Planned Analyses	
All eyes with attempted study lens (HMTIOL or HMIOL) implantation will be included in the safety analyses. The ECL comparison will include subjects with ECL data available for both eyes. The effectiveness outcomes will be summarized based on eyes implanted with HMTIOL or HMIOL. All data summaries will be performed based on observed data and not imputation for missing clinical outcomes will be performed. The analyses may be performed based on the per-protocol population and the best-case population (Section 8). For continuous variables, mean, standard deviation, median, minimum, and maximum will be provided for Cohort 1 and Cohort 2 separately. For categorical outcomes, the counts and percentages of eyes with each categorical level of outcomes will be summarized for Cohort 1 and Cohort 2 separately.
 
[REDACTED]
 
The ISO specified cumulative and persistent adverse events will be summarized at 3 months for Cohort 1 and Cohort 2 separately.
 
[REDACTED]
 
[REDACTED]

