### 3.2.3 EXCLUSION CRITERIA DURING SURGERY

1. Vitreous loss prior to use of the investigational device
2. Positive posterior pressure preventing safe implantation of the lens system
3. Anterior chamber hyphema preventing visualization of implantation
4. Any zonular or capsular rupture or capsular bag instability
5. Intraoperative miosis preventing visualization of fixation features
6. Need for concomitant procedures (e.g. glaucoma surgery, LRI, RK, LASIK, etc.)
7. Subject who, in the clinical judgment of the investigator, is not suitable for participation in the study for another clinical reason, as documented by the investigator

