## 8.2 ANALYSES POPULATIONS

Subjects that are screened but disqualified based on the preoperative and intra-operative eligibility criteria will be excluded from the safety and effectiveness data analyses. However, their reasons for the screen failure will be summarized. The analyses populations are defined below.

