### 8.2.1 SAFETY POPULATION

The **Safety Population** includes eyes with attempted study lens (HMTIOL or HMIOL) implantation, (successful or aborted after contact with the eye). The intraoperative and postoperative AEs and DDs will be summarized based on the safety population.

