7.1.1. SAFETY POPULATION

The Safety Population includes eyes with attempted study lens (HMTIOL or HMIOL) implantation, (successful or aborted after contact with the eye). The intraoperative and postoperative AEs and DDs will be summarized based on the safety population.

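### The opening rule of SAP 7 and Protocol 8.2 removes from the safety analyses subjects whose eyes the Safety Population definition keeps

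*SAP*

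**What the plan says.** SAP 7 begins: "Subjects that are screened but disqualified based on the preoperative and intra-operative eligibility criteria will be excluded from the safety and performance data analyses". The next sentence says what is kept of these subjects: "However, their reasons for the screen failure will be summarized". Protocol 8.2 has the same pair of sentences, with effectiveness in place of performance.

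The definition that follows in SAP 7.1.1 works by eye: "The Safety Population includes eyes with attempted study lens (HMTIOL or HMIOL) implantation, (successful or aborted after contact with the eye". Protocol 8.2.1 defines the population in the same way, and the Planned Analyses entry of the Protocol Synopsis states: "All eyes with attempted study lens (HMTIOL or HMIOL) implantation will be included in the safety analyses". SAP 5.5 bases the adverse event and device deficiency tables on this population.

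The intra-operative criteria are in Protocol 3.2.3. Criterion 1 is limited in time: "Vitreous loss prior to use of the investigational device". Criterion 4 is not: "Any zonular or capsular rupture or capsular bag instability".

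**The concern.** One rule takes subjects out of the safety analyses and the other keeps eyes in, and some eyes meet both. If the capsule ruptures while the study lens is being placed, the eye has had lens contact and belongs to the Safety Population. It also meets criterion 4, so the opening sentence removes the whole subject.

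The event that triggers the exclusion may then be the very event the safety table should count. Protocol 6.2 gives a capsular tear during implantation as an example of an adverse event, and Protocol 6.1.1 asks for particular attention to capsular injury and vitreous loss. For these events the error runs in one direction: removing the eyes that had the complication lowers its reported rate.

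The unit adds a second problem. The two eyes are operated on separate days, so a disqualification at the second surgery could remove a first eye that already holds a study lens, together with any events recorded in it.

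**Working it through.** **1. The rules side by side**

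| Place | Unit | Effect on the safety analyses |
|---|---|---|
| SAP 7 and Protocol 8.2, opening sentences | subject | out if disqualified on preoperative or intra-operative criteria; only the reason is reported |
| SAP 7.1.1 and Protocol 8.2.1 | eye | in if a lens was attempted, including attempts aborted after contact |
| Protocol Synopsis, Planned Analyses | eye | in if a lens was attempted |
| SAP 5.5 | eye | event and deficiency tables use the Safety Population |
| SAP 6 | subject | subjects without two successful implants leave the ECC comparison; safety is not mentioned |

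No text ranks the first row against the next three. SAP 2 puts the SAP above the Investigational Plan, but both rules stand in the SAP itself.

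**2. Can one eye meet both rules?**

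- Criterion 1 stops at device use. Criterion 4 and criterion 7 (investigator judgement) have no time limit, so either can be met after lens contact.
- Every Cohort 2 eye is to receive a lens and then undergo an exchange (Protocol 3.1, SAP 4). A rupture during the exchange comes after contact.
- Appendix A, Table 1 puts the second surgery 3 to 30 days after the first. Protocol 3.3.2 alternates which cohort goes first by odd or even subject number, so the implanted first eye may belong to either cohort.

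The overlap is therefore possible in both cohorts.

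**3. Denominators**

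SAP 6 needs 25 evaluable subjects and allows about 20% dropout: 25 / (1 − 0.20) = 31.25, rounded up to 32. This reproduces the planned 32 subjects, or 32 eyes per cohort and 64 in all. The allowance of 32 − 25 = 7 subjects covers intra-operative ineligibility and missing 3-month data together, so it is not a rupture rate.

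**4. Size, for assumed event counts**

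The documents give no rupture rate. Assume k = 1, 2 or 3 ruptures after lens contact, all in one cohort, in k different subjects, with lens contact in all 64 eyes.

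- Safety Population definition: k/32 in the cohort, k/64 over all eyes.
- Opening sentence: 0/(32 − k) in the cohort. Over all eyes it gives 0/(64 − 2k) when applied by subject, as written, and 0/(64 − k) if applied by eye.

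Intervals are exact two-sided 90%.

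| k | Cohort, definition | Cohort, sentence | All eyes, definition | All eyes, sentence by eye | All eyes, sentence by subject |
|---|---|---|---|---|---|
| 1 | 1/32 = 3.1% (0.2 to 14.0%) | 0/31 = 0% (0 to 9.2%) | 1/64 = 1.6% | 0/63 | 0/62 |
| 2 | 2/32 = 6.3% (1.1 to 18.4%) | 0/30 = 0% (0 to 9.5%) | 2/64 = 3.1% | 0/62 | 0/60 |
| 3 | 3/32 = 9.4% (2.6 to 22.5%) | 0/29 = 0% (0 to 9.8%) | 3/64 = 4.7% | 0/61 | 0/58 |

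**5. Second eye disqualified before any lens contact**

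Under the definition the second eye never enters the Safety Population and the implanted first eye stays. Under the sentence the first eye leaves too, and its cohort loses one eye from the denominator plus any event that eye had. If neither situation arises, the two rules give the same safety rates.

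**The case against.** The best defence is that the sentence is only a preamble. It speaks of screened subjects and screen failures and then announces that the populations are defined below. The definitions that follow explicitly keep attempts aborted after contact, the Synopsis says all eyes, and SAP 5.5 ties the tables to the named population. SAP 6 removes subjects with an intra-operatively ineligible eye from the ECC comparison and names no other exclusion. Protocol 3.3.2 treats a subject left without a study lens after an intra-operative complication as discontinued, not as a screen failure. Criteria 2, 3 and 5 concern conditions that prevent implantation or the surgeon's view, so criterion 4 can be read as a check made before implantation. The event counts above are assumed and show only that deleting every event gives zero.

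Most of this stands as evidence of intent. A programmer who builds each table from the named population would probably count the eyes correctly, and the size is conditional. It does not remove the conflict. The sentence names intra-operative criteria and the safety analyses outright. Protocol 3.3.1 enrols subjects at the preoperative visit, so every intra-operative disqualification comes after enrolment, and the screen-failure label does not settle the matter. SAP 6 does not say that the ECC comparison is the only analysis these subjects leave. A programmer who applies SAP 7 in the order written could drop subjects before forming the Safety Population.

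**Conclusion.** The sentence is wrong as written, in both documents, and the point is minor. Followed literally, it drops complications that arise after lens contact, and possibly an implanted fellow eye, from the summarised safety rates. One assumed event in a cohort of 32 eyes moves the rate from 3.1% to 0%; three move it from 9.4% to 0%. These figures rest on the assumed counts and on lens contact in every enrolled eye. The contradiction itself rests on neither.

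Individual adverse event reporting under Protocol 6 is not affected. This is a feasibility study with mainly descriptive safety summaries, and no planned comparison is claimed to change. SAP 5.5 does, however, set ISO event rates against reference rates and gives 90% intervals for HMTIOL-related events, so the set of eyes counted should be beyond doubt.

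**What to change.** Restrict the opening sentence in SAP 7 and Protocol 8.2. For example:

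*Subjects who fail preoperative eligibility, and eyes that fail an intra-operative criterion before any study lens or component has touched the eye, do not enter the safety or performance analyses; the reasons for screen failure are tabulated. Every eye touched by a study lens, and any implanted fellow eye, stays in the Safety Population.*

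In the protocol, write effectiveness for performance. The wider wording does no harm to the performance analyses, because the Implanted-Eye and Per Protocol definitions still decide which eyes are used there.

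The cost is one sentence edited in each document, with no added data, visits or subjects. The change concerns only which eyes are counted and alters no surgical decision.

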7.1.1. SAFETY POPULATION

The Safety Population includes eyes with attempted study lens (HMTIOL or HMIOL) implantation, (successful or aborted after contact with the eye). The intraoperative and postoperative AEs and DDs will be summarized based on the safety population.

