#### 5.3 ACCOUNTABILITY

The Investigator is responsible for keeping accurate accountability records of the number of study lenses received, dispensed, and returned to Sponsor. The study lenses must be stored under the appropriate conditions in a secure area and are to be implanted only in subjects enrolled in the study, in accordance with the conditions specified in this protocol.

All accountability records will include the following:

- Model and serial numbers
- Receipt date
- Quantities received
- Initials (attributability) of site personnel who received, dispensed, or returned study lenses
- Date of use
- Subject and eye treated with the study lens (by Subject ID and Initials only)
- Date returned to Sponsor
- Defective or damaged study devices

Periodically throughout the study and/or upon completion, the Sponsor (or designee) will review and verify the Investigator's accountability records. Following verification, and as directed by the Sponsor, all unused and explanted products must be returned to the Sponsor.

**Note:** In addition, any study lenses or components deemed defective, damaged, malfunctioning, or explanted must be retained by the site and returned to the Sponsor for evaluation. Under no circumstances are any components to be discarded or otherwise disposed of. If there is any question as to the applicability of this directive, consult the Protocol Contacts page of this protocol and discuss the situation with a Sponsor representative.

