#### 6.1.4 DEVICE DEFICIENCIES (DD)

A Device Deficiency (DD) is a failure of the device to meet its performance specifications or expectations, or otherwise not perform as intended. This can include either a malfunction or damage to the device or any part thereof, regardless of the source of malfunction or damage, including user error, and regardless of the presence of injury (or lack thereof) to subject, user, or bystander.

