5. Statistical Analyses*5.1. General Statistical Methods*

In general, analyses will be provided based on available data.

For continuous measures, descriptive summary statistics will include the number of observations, mean, standard deviation, median, minimum, maximum, as well as the number of eyes with results not reported. For continuous measures analyzed as changes from earlier visits, the 95% confidence interval for change will also be reported. Continuous measures may also be dichotomized or otherwise split into clinically meaningful categories and additionally analyzed as categorical measures.

For categorical measures, the percentage and number of cases for each condition (e.g., 20/40 or better) will be reported. The number of eyes without results will be omitted from the numerator and denominator of such calculations (i.e. no imputation will be performed).

Any calculated p-values will be based on nominal calculations with no adjustment for multiplicity. No imputation for missing data will be performed.

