5.5. Safety analyses

Adverse events and device deficiencies will be summarized at each study visit based on the safety population for Cohort 1 and Cohort 2 separately. The number and percentage of eyes reported with the ISO specified 3-month cumulative and persistent adverse events will be calculated for Cohort 1 and Cohort 2 separately.

Events will be summarized overall for the HMTIOL Cohort 2 and HMIOL Cohort 2. The corresponding one-sided lower 95% confidence limit will be calculated based on the binomial distribution and compared to the ISO SPE rate.

The number and percentage of eyes reported with HMTIOL-related adverse events during the study will be summarized for HMTIOL Cohort 1, HMTIOL Cohort 2, and HMTIOL-eye Cohort. The two-sided 90% confidence interval of the percentage will also be provided.

The number and percentage of eyes reaching BCDVA 20/40 or better, and worse than 20/40 at each visit will be prepared.

[figure not shown]
Rates for adverse events specified in ISO 11979-7:2014 Annex B for posterior chamber IOLs will be summarized at each visit.

Rates of device-related SSIs and device deficiencies will be summarized as described in 5.1 above.

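### The planned device-deficiency summary leaves out any deficiency found before the lens touches the eye when no study lens then touches that eye

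*SAP*

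**What the plan says.** Device deficiencies are a safety endpoint in the Protocol synopsis, Protocol 7.1 and SAP 5.4.

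SAP 7.1.1 fixes the analysis set, and Protocol 8.2.1 has the same rule: "The Safety Population includes eyes with attempted study lens (HMTIOL or HMIOL) implantation, (successful or aborted after contact with the eye". It continues: "The intraoperative and postoperative AEs and DDs will be summarized based on the safety population".

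SAP 5.5 gives the layout: "Adverse events and device deficiencies will be summarized at each study visit based on the safety population for Cohort 1 and Cohort 2 separately". It adds: "Rates of device-related SSIs and device deficiencies will be summarized as described in 5.1 above". For categorical measures SAP 5.1 states that "the percentage and number of cases for each condition (e.g., 20/40 or better) will be reported", and on missing results: "The number of eyes without results will be omitted from the numerator and denominator of such calculations".

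Capture of DDs is wider than this. Protocol 6.1.4 defines a DD as a failure of the device or any part of it, "regardless of the source of malfunction or damage, including user error, and regardless of the presence of injury". Contact with the eye is not a condition. Protocol 3.3.2 has sites record DDs seen before, during or after surgery. Protocol 6.3.1 requires all of them to reach the sponsor within 24 hours. The accountability records in Protocol 5.3 include "Defective or damaged study devices".

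**The concern.** A DD belongs to the device, but the summary admits it only through an eye that a study lens has touched. That rule suits adverse events, since a lens that never reached the eye cannot have harmed it. It does not suit a measure of whether the device arrives, loads and performs as specified. A lens damaged in loading is a DD under 6.1.4, and Protocol 3.3.2 allows a marketed lens to be used when the study lens is not implanted. That eye then contributes to neither numerator nor denominator.

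The summary sentence also names only intraoperative and postoperative DDs, although 3.3.2 has preoperative ones recorded too.

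The stake is a safety endpoint in a feasibility study of a modular lens, reported from a narrower set of events than the study collects, with the omission running in the favourable direction.

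A related reporting matter concerns Cohort 2. Its eyes undergo an optic exchange that Cohort 1 eyes do not, so they have more device handling per eye. The visible text does not separate DDs by surgical step.

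**Working it through.** **Step 1. Run the possible cases through SAP 7.1.1.**

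- Defect found before contact, and another study lens is then implanted. The eye is in the population and its DD can be counted, at least if it is classed as intraoperative. If it is classed as preoperative, the summary sentence does not name it.
- Defect found before contact, and no study lens then touches the eye. The eye is outside the population and the DD is omitted.
- Lens touches the eye and the attempt is then abandoned. The eye is in the population.
- Cohort 2, replacement optic found defective before contact, and the first optic is kept (3.3.2 provides for this). The first implantation succeeded, so the eye is in the population.

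The loss is therefore confined to the primary implantation step and to eyes that no study lens goes on to touch. Protocol 4.5 lists haptic or optic damage among events that can prevent implantation, so lens damage is foreseen, but it does not say whether the damage precedes contact.

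**Step 2. Direction.** Let x be the affected eyes among n in the population, and m the affected eyes left out. The planned percentage is x/n and the full one is (x + m)/(n + m). The difference is

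(x + m)/(n + m) − x/n = m(n − x) / [n(n + m)],

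which is never negative. The count of DDs is likewise reduced or unchanged.

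**Step 3. Scale.** The documents give no DD rate, count or threshold, so there is no DD figure to reproduce. The number of eyes follows from SAP 6: 25/(1 − 0.20) = 31.25, rounded up to 32 subjects, which matches the stated 32. That is at most 32 eyes per cohort. For illustration take m = 1 and n = 31:

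- x = 0: planned 0/31 = 0%; full 1/32 = 3.1%.
- x = 2: planned 2/31 = 6.5%; full 3/32 = 9.4%.

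The expected value of m cannot be computed from the documents.

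**Step 4. Why Cohort 2 should be split by step.** Suppose each optic has the same, independent DD probability p in both cohorts, with one optic per Cohort 1 eye and two per completed exchange eye. These are assumptions. The chance that an eye has at least one DD is p in Cohort 1 and 1 − (1 − p)² in Cohort 2:

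- p = 1%: 1.00% and 1.99%
- p = 3%: 3.00% and 5.91%
- p = 5%: 5.00% and 9.75%

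For p from 1% to 15% the ratio falls from 1.99 to 1.85. If the base counts as a further component at the same p (two against three components per eye), the ratio is 1.49 to 1.39; at 5% it is 14.26/9.75 = 1.46. Identical devices would thus show different per-eye figures.

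**Step 5. Repeats within an eye.** If eyes rather than events were counted, the expected number of hidden repeats in Cohort 2 would be 64p − 32[1 − (1 − p)²]. At 5% this is 3.20 − 3.12 = 0.08 events; at 15% it is 9.60 − 8.88 = 0.72. The effect is small unless DDs are common or cluster in an eye.

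**The case against.** The strongest reply is that the gap is narrow. It needs a defect found before contact and no later contact with any study lens, and the Protocol does not say that a loading defect leads there. Such a DD is still recorded, reported within 24 hours, kept in the accountability records and reviewed on receipt (Protocol 6.4). A reader might infer that it vanishes from the trial. It does not; only the planned summary omits it. This limits the harm but does not change the written rule.

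Three other readings are tempting and go beyond the text.

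- That several failures in one eye count once. SAP 5.1 speaks of cases and mentions eyes only when dealing with missing results. The explicit number-and-percentage-of-eyes wording in SAP 5.5 belongs to adverse events. The counting rule for DDs is undefined, and Step 5 shows that little turns on it.
- That a comparison of DDs between cohorts is invalid. None is planned in the visible text; the cohorts are summarised separately. The issue is only how adjacent figures will be read.
- That Cohort 2 handles exactly twice the optics. Two optics per exchange eye is an inference from Protocol 6.3.1, which treats exchanged optics as items to retain. The surgical guide is not among the documents, and an exchange may not be completed. The percentages in Step 4 rest on assumed rates.

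Parts of the safety text are not visible: SAP 5.7 shows only a heading, and a sentence in Protocol 8.3 is cut off. A full DD listing could stand there. The population sentence in SAP 7.1.1 is visible and explicit, however, and would still govern the summary.

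**Conclusion.** The concern holds as a mismatch between what is collected and what is summarised. DDs are defined, recorded and reported without regard to contact, while SAP 7.1.1 and Protocol 8.2.1 summarise only intraoperative and postoperative DDs in eyes that a study lens has touched. The effect on the endpoint is one-directional: it can understate DDs and cannot overstate them. The size of the loss is unknown. The figure of about 3 percentage points per omitted eye is illustrative and rests on 32 eyes in the cohort.

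The extra handling in Cohort 2 is a reason to present DDs by surgical step. It is not evidence of an error in a planned comparison.

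**What to change.** Give DDs their own rule in the SAP, and leave the Safety Population as it is for adverse events:

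- List and summarise every DD for every subject taken to surgery, including those found before surgery or before contact, with a column for whether the device touched the eye.
- Report the number of DDs beside the number of affected eyes, and state the eye denominator (eyes taken to surgery).
- In Cohort 2, show DDs at primary implantation separately from DDs at the optic exchange.
- If the accountability records allow, add a rate per optic or component used as a supportive figure. The record items in Protocol 5.3 have no explicit field for components opened, so this should not be the main denominator.
- Record the departure from Protocol 8.2.1 under SAP 9, or align the two texts.

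The cost is revised wording and one extra table. The main items need no new data collection, since the DD forms and surgical records already hold the information. The DD count may look slightly less favourable.
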